MedDRA	Medical Dictionary for Regulatory Activities
N	Number of Subjects
PP	Per Protocol
SAE	Serious Adverse Event
SAP	Statistical Analysis Plan
SAR	Serious Adverse Reaction
SD	Standard Deviation
SOC	System Organ Class
SUSAR	Suspected Unexpected Serious Adverse Reaction
TEAE	Treatment Emergent Adverse Event

2 Introduction

The statistical analysis plan (SAP) for the P-Monofer-IDA/CKD-EXT-01 trial is based on the final protocol 2.0 dated 14 June 2017.

The SAP describes in detail the analyses to be conducted and highlights any deviations from the analysis described in the protocol (see section 8). Deviations from methods described in this SAP, if any, will be specified in the clinical trial report.

Throughout this SAP treatment and baseline refers to treatment and baseline, respectively in this extension trial, unless otherwise specified.

Before releasing data for final analysis, one or more data review and classification meetings will be held to classify subjects with respect to analysis populations. The product of the classification meetings will be a detailed description of the analysis populations, and the number and nature of unresolved data queries will also be reported.

The analyses will be performed based on:

- The clinical database, which includes the electronic Case Report Forms (CRF)
- List of protocol deviations
- Analysis populations documented at the classification meetings

Reporting of the trials will be after the date of last subject last visit.

3 Trial Characteristics

3.1 Trial Objectives

3.1.1 Primary Objective

The primary objective of the trial is to evaluate the safety of IV iron isomaltoside after redosing.

3.1.2 Secondary Objectives

The efficacy objective of the trial is to evaluate the effect of iron isomaltoside on:

- Increase in haemoglobin (Hb)
- Other relevant iron related biochemical parameters

3.2 Trial Design

The trial is a prospective, open-label, multi-centre, extension trial of the lead-in trials; P-Monofer-IDA-01, P-Monofer-IDA-03, and P-Monofer-CKD-04.

The trial is a one-armed trial and all subjects will receive iron isomaltoside (Monofer[®]).

Table 1: Flow Chart

Visit	1 Screening	2 Baseline	3	4	5
Time (weeks)	-2	0	2	13	26
Visit window (days)		-	± 2	± 3	± 4
Informed consent	X				
Demographics	X				
In/exclusion criteria	X	X			
Eligibility lab tests	X ^c				
Pregnancy test, if relevant		X			
Medical history, including specific assessment of history of myocardial infarction, stroke, or congestive heart failure		X	X	X	X
Concomitant medication		X	X	X	X
Physical examination		X			X
Height		X			
Weight		X			X
Vital signs ^a		X	X	X	X
ECG ^a		X	X	X	X

Sponsor: Pharmacosmos	Date: 18-Jul-2018
Drug/Project: Monofer	Version: Final 2.0
Trial: P-Monofer-IDA/CKD-EXT-01	Statistical Analysis Plan

Safety lab tests		X	X	X	X
Efficacy lab tests		X	X	X	X
Treatment with iron isomaltoside		X			
Adverse events		X	X	X	X
Final visit form ^b					X

- a. For details of the assessment, please see Section 7.3.3.
- b. The final visit form may be filled in at any time of the trial if the subject is withdrawn.
- c. Laboratory tests taken at visit 6 of the lead-in trials P-Monofer-IDA-03 and P-Monofer-CKD-04 will be considered as screening values for the extension trial if they are collected ≤ 14 days before the screening visit.

3.3 Subject included

3.3.1 Sample Size Determination

No sample size calculations have been performed for this extension trial.

A target of 100 subjects will be recruited at selected sites with at least 25 subjects from P-Monofer-IDA-01 and P-Monofer-IDA-03 combined and at least 25 from P-Monofer-CKD-04. The distribution of subjects from each of the three trials does not need to be equal and the subjects will be enrolled consecutively based on the enrolment criteria until 100 subjects have been enrolled.

4 Analysis Populations

The following 4 analysis sets for subjects required in this extension trial are defined and will be used in the analyses of the data:

- Safety analysis set: The safety analysis set will include all subjects who received at least one dose of the trial drug.
- Intention to treat (ITT) analysis set: The ITT analysis set will include all subjects, with the exception of screening failures.
- Full Analysis Set (FAS): The FAS will consist of all subjects who received at least one dose of the trial drug in the lead-in trial (i.e. does not violate inclusion criteria 2), and have at least one post baseline Hb assessment.
- Per protocol (PP) analysis set: The PP analysis set will include all the subjects in the FAS who do not have any major protocol deviation of clinical or statistical significance. Major protocol deviations are defined in Section 4.1.

The classification of the subjects will be performed before database lock (DBL).

The primary analysis population for efficacy evaluation is the ITT analysis set. All efficacy endpoints will be presented using the ITT. If the FAS contains less than 90% of the subjects in the ITT set, then Hb will in addition be presented using FAS. Similar if the PP set contains less than 90% of the subjects in FAS (or ITT, if FAS is not presented), then Hb will in addition be presented using the PP analysis set.

4.1 Major protocol deviations

Deviations from the protocol will be registered as protocol deviations. Before DBL all protocol deviations will be evaluated and classified as minor, major, or GCP deviations. Protocol deviations classified as major will lead to exclusion from PP analysis set. The decisions will be documented.

The following will be assessed as major protocol deviation:

- Out of visit window of ≥ 30 days after the final visit (i.e. ≥ 212 days after baseline)
- Intake of prohibited medication
- Treatment compliance outside the 80-120 % range
- Other protocol deviations which are assessed as having a clinically or statistically significant effect

All major protocol deviations will be listed by subject and lead-in trial. Separate listings will be made for the ITT analysis set of visits 6 outside window of 14 days or more, intake of prohibited medication and treatment compliance outside range. Protocol deviations will be summarised by classification and category. The summary table will present number and percentages of subjects with a deviation and number of deviations.

4.1.1 Prohibited Medication

The following medication and non-drug therapy is not allowed:

- Any premedication (e.g. antihistamine or steroids) before administration of the trial drug. Daily treatment for e.g. allergy or asthma this is not considered as "premedication"
- Any iron supplementation other than investigational drug (nutritional supplementation including iron is allowed unless it is assumed as treatment of the subject's anaemia)
- Blood transfusion
- Erythropoiesis Stimulating Agents (ESA), unless the subject was treated with ESA in the lead-in trial or has received a stable dose (+/- 20 %) 4 weeks before the screening visit in this trial.

5 Planned Statistical Methods

5.1 Statistical Considerations

No formal hypotheses will be tested in this 6 months, one-armed, safety extension trial.

Baseline is defined as the last assessment with available data prior to the first administration of trial medication.

Categorical data will be summarized, using number and percentages of subjects. For calculation of percentages the denominator will be the number of subjects in the analysis set, unless otherwise stated. Numerical data will be presented using the number of subjects (n), mean, standard deviation (SD), median, lower quartile, upper quartile, minimum and maximum. Both the absolute values and the change from baseline will be presented, unless stated otherwise.

Sponsor: Pharmacosmos	Date: 18-Jul-2018
Drug/Project: Monofer	Version: Final 2.0
Trial: P-Monofer-IDA/CKD-EXT-01	Statistical Analysis Plan

Descriptive statistics for all endpoints will be presented overall and by lead-in trial and by week (if applicable) using observed cases, i.e. no imputation of missing data will be performed. All listings will be by lead-in trial and subject id unless stated otherwise.

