9.3 Subject Withdrawal

The subject has the right to withdraw from the trial at any time and for any reason without prejudice to his/her future medical care by the physician or at the institution. The PI can withdraw subjects from the trial in the following situations; treatment failure, safety reasons, and protocol violations.

The subject may also withdraw the consent if he/she does not wish to or is unable to continue in the trial. The Investigator will discuss with the subject the most appropriate way to withdraw in order to ensure the subject's health. If a subject withdraws from the trial, the Investigator will perform all final visit assessments, besides the scheduled trial assessments for that visit. Upon subject withdrawal, the Investigator will fill in the final visit form including the reason for withdrawal.

A subject who withdraws from the trial will not be re-enrolled or replaced with a new subject.

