5.2 Subject Disposition

An overall summary table of the subject disposition will be prepared with number and percentages of subjects in the following categories (and sub-categories):

- Screened subjects
- Analysis sets (ITT, safety analysis set, FAS, and PP analysis set)
- End of study status
- Withdrawn from trial including reasons

For calculation of the percentages the denominator will be number of subjects in the ITT.

Subject disposition will in addition be presented by lead-in trial. All information will be listed. Screening failures will be listed.

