7.4 Analysis and Presentation of the Secondary Efficacy Endpoints

The secondary efficacy endpoints are the following:

- Change in Hb from baseline to week 2 and months 3 and 6
- Change in s-ferritin, transferrin saturation (TSAT), and s-iron from baseline to week 2 and months 3 and 6

Change in Hb from baseline to week 2 and months 3 and 6 will be summarised by week using descriptive statistics overall and by lead-in trial for the ITT, and for the FAS and PP analysis sets, if applicable. Furthermore, change from baseline for the lead-in trial to current baseline, week 2 and months 3 and 6 including absolute Hb values will be summarised. Change in Hb concentrations over time will be presented using mean plots overall and by lead-in trial. Serum (s)-ferritin, TSAT and s-iron will be presented in similar ways using the ITT analysis set, only.

The efficacy data will be listed by lead-in-trial, subject and time point.

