7.5 Handling of Missing Values

No imputation of missing values will be applied.

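### Observed-case Hb summaries at months 3 and 6 may overstate the Hb gain if treatment failures withdraw, and the SAP does not say how the Hb taken at withdrawal is used

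*SAP*

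**What the plan says.** SAP 5.1 sets the general rule: descriptive statistics for all endpoints, "using observed cases, i.e. no imputation of missing data will be performed". SAP 7.5 repeats it: "No imputation of missing values will be applied". For haemoglobin, SAP 7.4 states: "Change in Hb from baseline to week 2 and months 3 and 6 will be summarised by week using descriptive statistics". SAP section 4 adds: "The primary analysis population for efficacy evaluation is the ITT analysis set". The FAS and PP repeats for Hb are produced only when those sets fall below 90% of the comparison set. They do not deal with a missing value at a visit. No sensitivity analysis for missing Hb is planned.

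Protocol 9.3 covers withdrawal: "The PI can withdraw subjects from the trial in the following situations; treatment failure, safety reasons, and protocol violations". The protocol does not define treatment failure. The same section also lets the subject leave for any reason, and it continues: "If a subject withdraws from the trial, the Investigator will perform all final visit assessments, besides the scheduled trial assessments for that visit". The visit 5 schedule (Protocol 6.7) includes the efficacy laboratory tests, and Protocol 7.10.3 lists Hb among them. On replacement, Protocol 9.3 says: "A subject who withdraws from the trial will not be re-enrolled or replaced with a new subject".

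SAP 5.2 includes in the disposition table: "Withdrawn from trial including reasons".

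**The concern.** Each subject receives one infusion and is followed for 26 weeks. Protocol 11.2 bars other iron treatment and transfusion during the trial and restricts ESA. A subject whose Hb falls and who needs one of these therapies must therefore either leave the trial or take a prohibited treatment. The second is a major deviation under Protocol 17.3, and protocol violations are themselves a ground for withdrawal. Low Hb can thus lead to exit by more than one route.

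If those subjects have no value at month 3 or month 6, the means at those visits describe the subjects who stayed. The ITT label does not prevent this, because a subject without a value at a visit drops out of that visit's mean. There is no control arm against which a selection effect would show. Protocol 20.1 names Hb change at these visits as a key secondary endpoint for public posting, where readers will see the means and not the subject listings.

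**Working it through.** **No figure to reproduce.** The documents state no expected Hb change, SD, dropout rate or power, so the size can only be shown as a range under stated assumptions.

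**Step 1: identity.** For any visit, let d be the share of subjects missing and let the gap be the mean change in observed subjects minus the mean change in missing subjects. Then

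bias = observed-case mean − all-subject mean = d × gap.

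| Missing (d) | gap −1.0 g/dL | gap 0 | gap 0.5 | gap 1.0 | gap 2.0 |
|---|---|---|---|---|---|
| 5% | −0.05 | 0 | +0.025 | +0.05 | +0.10 |
| 10% | −0.10 | 0 | +0.05 | +0.10 | +0.20 |
| 20% | −0.20 | 0 | +0.10 | +0.20 | +0.40 |

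For example, 0.10 × 1.0 = 0.10 g/dL. The identity holds for month 3 and month 6 alike. The sign is positive only when the missing subjects did worse than the observed ones.

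**Step 2: simulation for month 6.** All inputs are assumed; none comes from the documents.
- Mean Hb change of 0.5, 1.0 and 0.8 g/dL at week 2, month 3 and month 6.
- SD 1.2 g/dL and correlation 0.7 between adjacent visits.
- Withdrawal between months 3 and 6 by a logistic model on month-3 Hb change, with log-odds of 1.5 per SD, which is 1.5 / 1.2 = 1.25 per g/dL.
- 400,000 simulated subjects.
- The month-3 value stands in for the Hb taken at withdrawal.

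Bias at month 6 (g/dL):

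| Who leaves | Missing | Observed cases | Estimate using earlier Hb (MAR) | Withdrawal Hb placed at month 6 |
|---|---|---|---|---|
| Poor responders | 5% | +0.054 | 0.000 | −0.012 |
| Poor responders | 10% | +0.102 | 0.000 | −0.020 |
| Poor responders | 20% | +0.191 | +0.001 | −0.025 |
| Unrelated to Hb | 5% | 0.000 | 0.000 | +0.010 |
| Unrelated to Hb | 10% | 0.000 | 0.000 | +0.020 |
| Unrelated to Hb | 20% | −0.001 | 0.000 | +0.040 |
| Better responders | 5% | −0.053 | 0.000 | +0.032 |
| Better responders | 10% | −0.101 | 0.000 | +0.060 |
| Better responders | 20% | −0.191 | −0.001 | +0.105 |

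The poor-responder rows agree with step 1: 0.054 / 0.05 = 1.08, 0.102 / 0.10 = 1.02 and 0.191 / 0.20 = 0.96, so this selection model implies a gap of about 1 g/dL.

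**Step 3: strength of selection.** With the same SD and correlation and 8.4% to 17.7% withdrawn, the observed-case bias is +0.04 to +0.09 g/dL under weak selection (log-odds 0.5 per g/dL) and +0.11 to +0.21 g/dL under strong selection (2 per g/dL).

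**Step 4: the withdrawal Hb.** The last column of the table in step 2 shows that the result depends on a choice the SAP leaves open. When poor responders leave, placing the withdrawal value at month 6 removes the upward bias. It is not neutral in general: with withdrawal unrelated to Hb and 20% missing, it adds 0.20 × (1.0 − 0.8) = 0.04 g/dL, because an earlier value is counted as a later one.

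**Limits.** The simulated withdrawals all fall after month 3, so step 2 says nothing about month 3; there only the identity in step 1 applies. The model-based estimate is unbiased here because dropout was generated to depend only on an observed Hb. That is an assumption, not evidence about this trial.

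**The case against.** The strongest objection is that Protocol 9.3 itself requires the final-visit assessments at withdrawal, so an Hb at exit should normally exist. If it enters the later summary, the upward bias largely disappears under the assumptions above. This stands, and it moves part of the point: the SAP does not say whether that value goes to a scheduled visit, is shown separately or is left out.

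A reader might infer that the reported gain will be biased upward. The documents do not support that. Withdrawal for treatment failure is permitted, not required. It stands beside safety reasons, protocol violations and the subject's own choice, and the sign reverses if better responders leave. A reader might also take a bias near 0.2 g/dL as typical. That needs roughly 20% missing, or strong selection with about 18% missing, and neither figure is in the documents.

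It is also fair that observed-case description is a legitimate choice in a single-arm trial with no hypothesis test, that the primary endpoint is adverse drug reactions, and that the stated efficacy objective is an increase in Hb rather than its durability. The SAP already reports reasons for withdrawal, n with each summary and subject-level efficacy listings. These let a reader suspect selection. They do not provide an adjusted mean, and they do not settle the use of the withdrawal Hb.

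**Conclusion.** The point holds in a limited form. Observed-case Hb means at months 3 and 6 may overstate the gain if subjects withdrawn for treatment failure are missing from them. The plan has no supportive analysis for this and no rule for the Hb taken at withdrawal.

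For month 6 the size runs from zero, when withdrawal is unrelated to Hb, to about +0.2 g/dL, when poor responders leave and up to 20% are missing. It is negative if better responders leave. These figures rest on an assumed SD, correlation, mean changes and selection model. For month 3 only the general identity is available. The primary safety endpoint is unaffected and no formal conclusion depends on Hb, so the change is worth making but modest.

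**What to change.** Keep the observed-case table as planned. In SAP 7.4:

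1. Add one supportive mixed model for repeated measures of Hb change, with visit, baseline Hb and lead-in trial as terms and an unstructured covariance. Report means with 95% confidence intervals at week 2 and months 3 and 6, with no hypothesis test.
2. State how an Hb taken at a withdrawal visit is assigned to visits, and whether it enters the observed-case table, the model, both or neither.

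The cost is one extra model and one sentence of specification, using data already collected. The downside is that the model relies on missing-at-random, which cannot be verified, and the reported gain may be slightly smaller.

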5.2 Subject Disposition

An overall summary table of the subject disposition will be prepared with number and percentages of subjects in the following categories (and sub-categories):

- Screened subjects
- Analysis sets (ITT, safety analysis set, FAS, and PP analysis set)
- End of study status
- Withdrawn from trial including reasons

For calculation of the percentages the denominator will be number of subjects in the ITT.

Subject disposition will in addition be presented by lead-in trial. All information will be listed. Screening failures will be listed.

5.3 Baseline Characteristics and Demographics

Demographics and baseline characteristics consist of age, gender, ethnic origin, and smoking habits. Age will in addition be grouped into: 18-64 years, 65-84 years and above 84 years. Demographics will be listed and summarized using descriptive statistics, overall and by lead-in trial for the ITT analysis set. Age, Age groups and sex will in addition be presented by the FAS, safety analysis set and PP population.

5.4 Medical History

Relevant medical history is collected and will be summarised and listed. The summaries will be made by system organ class (SOC) and preferred term and by preferred term for the ITT analysis set. Separate summary and listing will be made of underlying disorder causing IDA.

6 Exposure and Other Dosing Information

6.1 Exposure

Dose and compliance will be summarized using descriptive statistics and presented for the safety analysis set overall and by lead-in trial.

For actual dose will be presented including dose category, dose in mg, number of doses and compliance.

Compliance will be calculated as:
$$\frac{100 \times \text{actual dose}}{\text{planned dose}}$$

All information will be listed by lead-in trial and subject. Furthermore, subjects out of the treatment compliance range of 80-120 % will be listed.

6.2 Concomitant medication

Concomitant medication at baseline and changes in concomitant medication during the trial will be recorded. All concomitant medication will be summarised and listed using the ITT analysis set. The summaries will be made by anatomical therapeutic chemical (ATC) term. The listing will be by lead-in trial and subject.

7 Statistical Methodology for Primary and Secondary Endpoints

7.1 Analysis and Presentation of the Primary Endpoint

The primary endpoint is the number of adverse drug reaction (ADR), defined as adverse events (AEs) that are related or possibly related to trial drug.

Overall number and percentages of subjects with ADRs and number of ADRs will be summarized overall and by lead-in-trial, including two-sided 95 % exact Clopper-Pearson confidence limits (CL) for the number of subjects reporting ADRs.

7.2 Secondary Safety Endpoints

The secondary safety endpoints are the following:

- Serious or severe hypersensitivity reaction starting on or after the treatment with iron isomaltoside (i.e. treatment-emergent). The hypersensitivity terms are defined as standardised Medical Dictionary for Regulatory Activities query (SMQ) terms (including four additional terms) in protocol Appendix A.
- Composite cardiovascular AEs starting on or after the treatment with iron isomaltoside (i.e. treatment-emergent). The adjudicated composite AEs includes the following:
 - Death due to any cause
 - Non-fatal myocardial infarction
 - Non-fatal stroke
 - Unstable angina requiring hospitalization
 - Congestive heart failure requiring hospitalization or medical intervention
 - Arrhythmias
 - Hypertension
 - Hypotension
- Time to first composite cardiovascular safety AE
- Serum (s-) phosphate < 2 mg/dL at any time from baseline to month 6

Additional safety assessments are physical examinations and measurements of vital signs, height, weight, electrocardiogram (ECG), and safety laboratory parameters.

7.3 Analysis and Presentation of the Safety Endpoints

7.3.1 Adverse Events

AEs will be coded using the Medical Dictionary for Regulatory Activities (MedDRA) current version. AEs will be regarded as treatment emergent AEs (TEAEs) if they occur after administration of iron

Sponsor: Pharmacosmos	Date: 18-Jul-2018
Drug/Project: Monofer	Version: Final 2.0
Trial: P-Monofer-IDA/CKD-EXT-01	Statistical Analysis Plan

isomaltoside or occur before dosing and increase in severity after dosing. AEs that increase in severity from before till after dosing will be identified by means of Data Management Audit Trail. Non-treatment emergent AEs (Non-TEAE) are defined as AEs collected in the current trial, before dosing and does not increase in severity from before till after dosing. There will be more than 5 half-lives between dosing in the lead-in trial and screening in the current trial, thus none of the AEs will be regarded as related to previous treatment.

An overall summary table by treatment will be made. The overall summary table will include total number of events, total number of subjects, and proportion of subjects reporting AEs, non-TEAEs, TEAEs, Treatment emergent serious adverse events (SAEs), Fatal SAEs, ADRs, serious adverse reactions (SAR), TEAEs by severity, and TEAEs by outcome.

All TEAEs will be summarised by SOC and preferred term (PT). The summaries will include number of events, number of subjects, and proportion of subjects reporting these events and will be tabulated overall and by lead-in-trial for:

- TEAEs
- Non-serious TEAEs, frequency $\geq 5\%$ (or lower frequency as applicable)
- Treatment emergent SAEs
- TEAEs by severity (mild, moderate, severe)
- TEAEs by relationship (related, possible, unlikely, not related, unknown)
- ADRs
- SARs
- Composite cardiovascular TEAEs
- Serious or severe hypersensitivity reactions
- Hypersensitivity reactions

A two-sided 95 % exact Clopper-Pearson confidence limit (CL) for the overall number of subjects reporting SARs will be constructed.

The following listings of AEs will be made based on the safety analysis set:

- Non-TEAEs
- TEAEs (non-serious and serious)
- TESAEs
- ADRs (including SUSARs)
- AEs leading to dose reduction or withdrawal from treatment
- Fatal SAEs
- Serious or severe hypersensitivity reactions
- Hypersensitivity reactions
- Composite cardiovascular AEs

In addition, a listing of SAEs for subjects not in the safety analysis set will be made.

All data from adjudication review will be listed.

Sponsor: Pharmacosmos	Date: 18-Jul-2018
Drug/Project: Monofer	Version: Final 2.0
Trial: P-Monofer-IDA/CKD-EXT-01	Statistical Analysis Plan

Time to first composite cardiovascular AE is defined as the actual time in days from date of treatment till the date of the adjudicated AE. For subjects not reporting a composite cardiovascular AE, the time will be censored at the date of the last attended visit.

The time to first composite cardiovascular AEs will be estimated using the Kaplan-Meier method and presented in a plot.

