1.2 Definition of Terms

Baseline values	The “baseline” values are the values measured at the baseline visit, before first administration of the trial drug. For variables/assessments not performed on the baseline visit, the baseline value is the value from the screening period measured closest to the baseline visit.
Completed subject	A subject, who is enrolled in the trial after signing informed consent, exposed to trial drug, and not withdrawn or lost to follow up during the trial.
End of trial	The end of trial is the last subject last visit date.
Final subject visit	The final trial visit for a subject. No trial related procedure is performed after this visit.
Iron isomaltoside	Iron isomaltoside 1000 (Monofer [®])
Subject withdrawal	Time point when the subject exits from the trial prior to the planned completion of all trial drug administrations or assessments.
Screening period	The time period from signed informed consent until inclusion or exclusion from the trial.

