12.4 Collection of Adverse Events

The Investigator is responsible for ensuring that all AEs (as defined in Section 12.1) observed by the Investigator or reported by the subject are properly collected and recorded in the subject’s medical record as well as in the AE pages of the eCRF.

Screen failures: All SAEs will be reported in the eCRF from the time a subject has signed the ICF and until he/she exits the trial. Non-serious AEs occurring in subjects who are never treated with the trial drug will not be collected.

Treated subjects: From the time a subject has signed the ICF and until he/she exits the trial, all AEs/SAEs will be reported in the eCRF. AEs/SAEs occurring before administration of the trial drug are considered as non-treatment emergent, and those occurring after administration of the trial drug are considered as treatment emergent.

If a subject is permanently withdrawn from the trial because of an AE, this information must be included in the final visit form.

An AE should be described in the following manner: The nature of the event will be described in precise, standard medical terminology (i.e. not necessarily the exact words used by the subject). If known, a specific diagnosis should be stated. Furthermore, the Investigator should describe an AE regarding seriousness (see Section 12.2), severity, relatedness, action taken, and outcome.

Severity

- Mild: The AE does not interfere in a significant manner with the subject's normal functioning level, but may be an annoyance
- Moderate: The AE produces some impairment of functioning but is not hazardous to health, but is uncomfortable and/or an embarrassment
- Severe: The AE produces significant impairment of functioning or incapacitation and is a hazard to the subject

Relatedness

- Related: The AE is related to the medicinal product
- Possible related: A causal relationship is conceivable and cannot be dismissed
- Unlikely related: The event is most likely related to an aetiology other than the medicinal product
- Not related: No relatedness to the medicinal product

The categories "related" and "possible related" will be classified as related AEs and the categories "unlikely related" and "not related" will be classified as unrelated AEs in the clinical study report (CSR).

Outcome

- Recovered/resolved: Complete clinical recovery without any sequel attributable to the event as per Investigator's discretion

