12.5 Reporting of SAEs

The Investigator must report all SAEs promptly and within **24 hours** to Drug Safety at Pharmacosmos A/S after obtaining knowledge of the event.

The Investigator should report the SAEs by filling out the SAE form and report to Pharmacosmos A/S either by e-mail at **[contact]** or **[contact]**.

Contact details: Drug Safety, Pharmacosmos A/S
[name]
Phone: +
[contact]
E-mail: [contact]

After the initial SAE report, the Investigator is required, proactively, to provide further information regarding the subject's condition. All follow-up information must be forwarded to Pharmacosmos A/S as it becomes available.

For all AEs with fatal outcome, autopsy reports (if available) and relevant medical reports should be reported to Pharmacosmos A/S, as described above.

SAEs occurring after trial termination must be reported if considered related to the trial treatment.

Pharmacosmos A/S will report SUSARs to the Competent Authorities within 7 calendar days for fatal and life threatening SUSARs and follow-up information within the next 8 calendar days. All other SUSARs are submitted as soon as possible within 15 calendar days and relevant follow-up information is subsequently communicated as soon as possible.

Pharmacosmos A/S will inform any SUSARs to all PI(s) within 15 calendar days by circulating the Council for International Organizations of Medical Sciences (CIOMS-I) form.

All SAEs including expected SARs will be reported by Pharmacosmos A/S to the Competent Authorities by the annually Development Safety Update Report.

In addition, 6-monthly safety reports will be prepared by Pharmacosmos A/S and submitted to the Investigators for information.

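### Time to first cardiovascular AE: events have no end date but event-free subjects are censored at the last attended visit, a mismatch for subjects who leave without a final visit

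*SAP*

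**What the plan says.** SAP 7.3.1 defines the event time as "the actual time in days from date of treatment till the date of the adjudicated AE". It gives no latest date for a counted event. For subjects without an event, "the time will be censored at the date of the last attended visit". The time to first event "will be estimated using the Kaplan-Meier method and presented in a plot".

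Protocol 12.4 sets the collection window for treated subjects: "From the time a subject has signed the ICF and until he/she exits the trial, all AEs/SAEs will be reported in the eCRF". Protocol 12.5 goes further: "SAEs occurring after trial termination must be reported if considered related to the trial treatment".

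Two other provisions limit the gap. Protocol 1.2 defines the final subject visit as "The final trial visit for a subject. No trial related procedure is performed after this visit". Protocol 9.3 says: "If a subject withdraws from the trial, the Investigator will perform all final visit assessments". Loss to follow-up is foreseen all the same, because Protocol 1.2 describes a completed subject as "exposed to trial drug, and not withdrawn or lost to follow up during the trial".

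Visits after dosing are at weeks 2, 13 and 26 (Protocol, Table 1).

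**The concern.** In a Kaplan-Meier analysis, events and event-free time should be observed over the same window. Here the window closes at the last visit if nothing happened, but stays open if something did. Take a subject who leaves in week 25 without a visit after week 13. An event in week 20 would count. Without an event, the same subject leaves the risk set at week 13. Censoring then depends on the outcome, and the direction is upward: late events are kept while late event-free time is dropped.

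Time to first composite cardiovascular AE is a named secondary safety endpoint in a trial whose primary objective is safety. The composite includes death from any cause, which can become known without a visit.

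**Working it through.** The plan has no figure to reproduce: neither document gives an event rate, a dropout rate or a sample size calculation.

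**Step 1: who has a gap between the two dates**

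- Completer: the last attended visit is the final visit, so the gap is 0.
- Withdrawal with the Protocol 9.3 assessments done at exit: the gap is 0.
- Subject lost, or leaving without a visit: the gap runs from the last visit to the last date with AE status known. For an exit at week 25 after a last visit at week 13, it is 175 − 91 = 84 days. If only baseline was attended, censoring is at day 0.
- Subject with a counted event after the final visit: the event lies beyond the date at which the same subject would otherwise have been censored.

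**Step 2: mean gap for a subject leaving without a visit**

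Visits are at days 0, 14, 91 and 182 (weeks × 7). Assume that exit times are uniform over 182 days and that AE status is known up to exit. The intervals are 14, 77 and 91 days, so

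mean gap = (14² + 77² + 91²) / (2 × 182) = 14,406 / 364 = 39.6 days.

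**Step 3: share of person-time lost**

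Let d be the dropout proportion and s the share of dropouts without an exit visit. Ignoring the small effect of events on follow-up,

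f = d × s × 39.6 / [182(1 − d) + 91d].

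**Step 4: shift in the six-month risk**

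With a constant hazard, the same events over a fraction (1 − f) of the person-time turn a risk p into approximately 1 − (1 − p)^(1/(1 − f)). The last column is a simulation of the SAP rule against censoring at exit, with 400,000 subjects per scenario.

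| p | d | s | f | shift, formula | shift, simulated |
|---|---|---|---|---|---|
| 10% | 10% | 0 | 0 | 0 | 0.00 points |
| 10% | 10% | 0.5 | 1.98/172.9 = 1.1% | 0.11 | 0.11 points |
| 10% | 10% | 1 | 3.96/172.9 = 2.3% | 0.22 | 0.22 points |
| 10% | 20% | 0.5 | 3.96/163.8 = 2.4% | 0.23 | 0.23 points |
| 10% | 20% | 1 | 7.92/163.8 = 4.8% | 0.48 | 0.48 points |
| 20% | 20% | 1 | 4.8% | 0.90 | 0.89 points |

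The last row is the largest shift in a grid of 5-20% risk and 0-20% dropout. In the 10% risk scenarios, censoring at exit gave 9.9% to 10.1%. Ending both events and censoring at the last visit agreed with that to within 0.03 points, so either common date removes the bias.

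**Step 5: comparison with sampling error**

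With 100 subjects and 10% risk, SE = √(0.10 × 0.90 / 100) = 3.0 points. The largest shift at 10% risk is 0.48 / 3.0 = 0.16 of one standard error.

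**Step 6: an event after the final visit**

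The simulation does not cover this case. Visit 5 falls between days 178 and 186 (182 ± 4). If all final visits are in window and one subject has a counted event after day 186, that subject is alone in the risk set. The survival estimate is multiplied by 1 − 1/1 = 0, so the plotted curve drops to zero at its end. The curve up to day 178 does not change.

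**The case against.** The strongest objection is that the protocol largely closes the gap itself. Final visit assessments are required at withdrawal and a completer's participation ends at the final visit, so for most subjects the last attended visit is the exit. That stands. A reader might infer from SAP 7.3.1 that person-time is cut and the risk overstated across the whole trial. The documents do not support that: Step 4 gives zero when every exit has a visit.

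Scheduled AE evaluation also takes place only at visits, and neither document mentions telephone follow-up. Where nothing is known after the last visit, censoring there is correct. That stands too. It does not cover events that become known between visits, since SAEs must be reported within 24 hours of the investigator's knowledge. Nor does Protocol 9.3 guarantee a visit from someone lost to follow-up.

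Little depends on the result. The output is a plot, no hypothesis is tested, and the counts and proportions of subjects with composite cardiovascular AEs do not use censoring dates. A constant hazard is also doubtful, because Appendix B counts blood pressure changes straight after the infusion, and later censoring hardly affects such early events.

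On events after trial termination, the documents do not say whether these SAEs would enter the clinical database or be adjudicated. The tail effect in Step 6 is possible under the stated rule but not certain.

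**Conclusion.** The concern holds in a limited form. Events and event-free time end on different dates. The mismatch has an effect only for subjects who leave without a final visit but whose later events can still become known, or who have a counted event after the final visit. There the curve can be biased upward; elsewhere it is not.

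At 10% risk and 10-20% dropout, half to all without an exit visit, the shift is about 0.1 to 0.5 points, small against a standard error of about 3 points. These rates are assumptions, as are constant hazard, uniform exit times and dropout unrelated to risk. If subjects lost without a visit differ in risk, the size could change. No conclusion of the trial depends on this point. It is worth correcting because one sentence does it.

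**What to change.** In SAP 7.3.1, define one end date per subject and apply it to both outcomes: censor event-free subjects at the last date with AE status known, and count events only up to that date. The date should come from visits or contacts that would have taken place with or without an event; a date known only because an event was reported would bring the asymmetry back. An administrative exit date should not be used for a lost subject, because it adds event-free time that nobody observed and pulls the risk down.

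Before choosing this option, check that the eCRF holds such a date. On withdrawal, Protocol 9.3 names only the reason as an item of the final visit form. If the date is not recorded, count events only up to the last attended visit and keep the present censoring rule.

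The cost is one extra derived date. Under the fallback, a few late events are left out of the curve, but they remain in the AE tables and listings and can be footnoted on the plot.
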